### **11.0 STATISTICAL CONSIDERATIONS**

#### **11.1 Study Design/Study Endpoints**

This is a prospective, single-arm, multi-site study evaluating combination trabectedin and olaparib. Eligible patients will be assigned to one of two cohorts. Cohort 1 consists of patients with leiomyosarcoma or liposarcoma. Cohort 2 consists of patients with other bone or soft tissue sarcoma histologies. An independent Simon-minimax two-stage design will be used in each cohort.

The primary objective is to estimate the overall response rate (CR+PR) with an endpoint of objective response as based on RECIST 1.1 criteria anytime within a minimum of 18 months after start of treatment but no more than 2 years from registration. Secondary endpoints include PFS, OS and occurrence of adverse events. Exploratory endpoints include the presence of DNA repair defects by NGS and/or IHC and cardiovascular biomarkers.

#### **11.2 Sample Size and Accrual**

In cohort 1, based on currently available phase III data, the ORR for LMS/LPS subgroup to trabectedin monotherapy (including best response of complete or partial response) is 9% with a 43% clinical benefit rate (CBR). Therefore, we will target a RR of 25% with trabectedin plus olaparib to conclude that combination therapy is meaningful. In stage 1,

we will enroll 16 patients. If  $\leq 1$  patient had an objective response in the first stage, we will terminate the trial early. If  $> 1$  patients have an objective response in the first stage, then an additional 10 patients will be enrolled in stage 2, for a total of 26 patients. If  $\geq 5$  out of 26 patients have an objective response, then we will declare that the combination is promising and worthy of further study. The type 1 error rate is 10% and the power is 80%.

In cohort 2, the ORR is approximately 5% to trabectedin monotherapy. Therefore, we will target a RR of 20% for the combination to be meaningful. In stage 1, we will enroll 13 patients; if zero patients had an objective response, we will terminate the study early. Otherwise, if  $\geq 1$  patient had an objective response, we will enroll an additional 14 patients in stage 2, for a total of 27 patients. If  $\geq 4$  out of 27 patients have an objective response, then we will declare that the combination is promising and worthy of further study. The type 1 error rate is 5% and the power is 80%.

In cohort 1, we require a minimum of 16 patients and a maximum of 26 patients. Assuming we can enroll 2 LMS/LPS patients per month, we will require a minimum of 9 months and a maximum of 14 months to complete accrual. Assuming we will follow the last patient for an additional 24 months, the expected study duration for cohort 1 is expected to be between 33 and 38 months.

In cohort 2, we require a minimum of 13 patients and a maximum of 27 patients. Assuming we can enroll 2 patients with other sarcoma histologies per month, we will require a minimum of 7 months and a maximum of 14 months to complete accrual. Assuming we will follow the last patient for an additional 24 months, the expected study duration for cohort 2 is expected to be between 31 and 38 months.

The total expected duration to complete accrual and follow-up for cohorts 1 and 2 is 33 and 38 months.

### **11.3 Data Analyses Plans**

To address the primary objective, the overall response rate will be calculated as the proportion (and exact binomial 95% confidence interval) of patients with complete or partial response as defined by RECIST 1.1, within each cohort.

To address the secondary objectives:

- a. Progression free survival (PFS) will be calculated by the Kaplan-Meier method with errors according to Peto, within each cohort. Median and 6-month PFS will be estimated along with their 95% confidence intervals.
- b. Overall survival (OS) will be calculated by the Kaplan-Meier method with errors according to Peto, within each cohort. Median, 1- and 2-year OS will be estimated along with their 95% confidence intervals.
- c. The frequency and rates of adverse events occurring in at least 5% of participants and rates of grade 3-5 adverse events will be tabulated by system organ class and preferred term using Common Terminology Criteria of Adverse Events (CTCAE), within each cohort.

To address the exploratory objectives:

- a. The frequency and proportion of alterations in tumor sequencing will be summarized within each cohort.
- b. The frequency and proportion of alterations in DNA damage repair pathways will be summarized within each cohort.
- c. Changes in levels of novel cardiovascular biomarkers will be summarized and compared to clinical and echocardiographic cardiotoxicity.

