Key Exclusion Criteria	
 
• Prior therapy with PARP inhibitor
 
• Prior therapy with trabectedin
 
• Additional active malignancy or treatment for alternative cancer (excluding non-melanoma skin cancer) requiring treatment within the past two years
 
• Pregnant or breastfeeding women
 
• Known hypersensitivity to trabectedin
 

Study Product(s), Dose, Route, Regimen	Olaparib 150 mg PO BID continuously Trabectedin 1.1 mg/m  IV every 21 days
Duration of Administration	Treatment consists of 21-day cycles. Therapy will continue until disease progression or patient meets one of the off-study criteria for a maximum of 18 months.
Reference Therapy	No comparator. Historical controls of single agent trabectedin in soft tissue sarcoma.
Statistical Methodology	
A Simon Minimax two-stage design is utilized for this study. Based on currently available phase III data, the ORR for LMS/LPS subgroup to trabectedin monotherapy is 9%. We will target a response rate (RR) of 25% with combination trabectedin and olaparib. In cohort 2, the ORR is approximately 5% with trabectedin monotherapy. We will target a RR of 20% for this combination. This trial is designed with a type 1 error of 10% in cohort 1 and 5% in cohort 2 with a power of 80%.
 
Cohort 1: 16 patients will be enrolled in stage 1. If <math>\leq 1</math> patient has an objective response, we will terminate the study. If <math>> 1</math> objective response, an additional 10 patients will be enrolled. If <math>\geq 5</math> of 26 patients have an objective response, we will declare the combination as promising and worthy of further study.
 
Cohort 2: 13 patients will be enrolled in stage 1. If 0 patients have an objective response, we will terminate the study. If <math>\geq 1</math> objective response, an additional 14 patients will be enrolled. If <math>\geq 4</math> of 27 patients have an objective response, we will declare the combination as promising and worthy of further study.

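### Section 11.3 estimates the primary response rate as if each cohort were a single sample, so the proportion is biased slightly downward and the exact 95% interval ignores the stage 1 futility stop

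*Combined protocol and SAP*

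**What the plan says.** Section 11.1 states the design: "An independent Simon-minimax two-stage design will be used in each cohort". Section 11.2 gives the rules.

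- **Cohort 1:** null 9%, target 25%. Stop at 1 or fewer responses in 16; otherwise enrol 10 more, and succeed at 5 or more of 26. Type 1 error 10%, power 80%.
- **Cohort 2:** null 5%, target 20%. Stop at 0 of 13; otherwise enrol 14 more, and succeed at 4 or more of 27. Type 1 error 5%, power 80%.

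On reaching the threshold, the synopsis says "we will declare the combination as promising and worthy of further study".

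The primary objective (2.1 and 11.1) is worded as estimating the response rate. The whole analysis for it, in 11.3, is the proportion with complete or partial response and its "exact binomial 95% confidence interval", within each cohort. No stage-adjusted estimate or interval appears anywhere, and nothing says how the interval should be read beside the count rule. The documents do not use the terms one-sided or single-sample. The first is inferred from a rule that succeeds only on high counts, the second from the plain wording of 11.3.

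**The concern.** An exact binomial interval is exact for a fixed sample size. Here the sample size depends on the data: a cohort with few early responses stops at 16 or 13 patients, and a cohort with more goes on to 26 or 27. A low stage 1 result is therefore frozen without the later patients who would on average pull it back toward the true rate. This biases the pooled proportion downward. The set of possible outcomes also mixes two sample sizes, and the fixed-sample interval does not account for that.

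Since the stated objective is estimation, the estimate and its interval are the trial's main numerical result. They will be read against the monotherapy rates of 9% and 5% that the protocol itself names. A reader who finds 9% inside the interval of a cohort declared promising needs to know in advance which of the two governs.

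**Working it through.** **Inputs.** From 11.2: cohort 1 n1 = 16, r1 = 1, n2 = 10, N = 26, p0 = 9%, p1 = 25%. Cohort 2 n1 = 13, r1 = 0, n2 = 14, N = 27, p0 = 5%, p1 = 20%. From 11.3: raw proportion and Clopper-Pearson 95% limits.

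**1. The plan's own figures.** P(success) = Σ over x > r1 of P(X1 = x) · P(X2 ≥ threshold − x). Cohort 1: 0.0756 at 9% and 0.8029 at 25%. Cohort 2: 0.0416 at 5% and 0.8011 at 20%. A full minimax search returns exactly the stated designs, so the stated error rates hold.

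**2. Bias of the raw proportion.** If a cohort stops, the reported X1/n1 replaces a full-sample proportion whose expected value would be (X1 + n2·p)/N. Hence bias = (n2/N) · Σ over x ≤ r1 of P(X1 = x)(x/n1 − p).

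- Cohort 1 at 9%: (10/26)[0.2211(−0.09) + 0.3499(0.0625 − 0.09)] = (10/26)(−0.0295) = −1.1 points.
- Cohort 1 at 25%: (10/26)[0.0100(−0.25) + 0.0535(0.0625 − 0.25)] = (10/26)(−0.0125) = −0.5 points.
- Cohort 2 at 5%: (14/27)(0.95^13)(−0.05) = (14/27)(0.5133)(−0.05) = −1.3 points.
- Cohort 2 at 20%: (14/27)(0.0550)(−0.20) = −0.6 points.

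**3. Unbiased estimate.** For s responses after stage 2, UMVUE = Σ C(n1−1, x−1)C(n2, s−x) / Σ C(n1, x)C(n2, s−x), over x > r1. If the cohort stops at stage 1 it equals the raw proportion. The two-stage limits below rank every stage 1 stop below every stage 2 outcome.

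| Result | Raw | UMVUE | Single-sample 95% | Two-stage 95% |
|---|---|---|---|---|
| 2/26 | 7.7% | 15/120 = 12.5% | 0.9–25.1% | 1.6–30.6% |
| 5/26 | 19.2% | 12,440/62,168 = 20.0% | 6.6–39.4% | 6.6–39.6% |
| 6/26 | 23.1% | 23.4% | 8.97–43.6% | 9.004–43.7% |
| 4/27 | 14.8% | 2,600/16,549 = 15.7% | 4.2–33.7% | 4.3–34.1% |

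**4. Coverage of the planned interval under the two-stage design.** Cohort 1: 99.3% at 9% and 97.5% at 25%. Cohort 2: 99.0% at 5% and 98.1% at 20%. At a true 25% in cohort 2, the outcomes whose interval misses are:

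- 0/13 (upper limit 24.7%), probability 0.75^13 = 0.0238;
- 1/27 (upper limit 19.0%), 0.0018;
- 2/27 (upper limit 24.3%), 0.0122;
- 12 or more of 27, 0.0216.

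The sum is 0.0594, so coverage is about 94.0% to 94.1%. The low-side misses total 0.0238 + 0.0018 + 0.0122 = 0.0378, above the intended 0.025, because the stage 1 stop and the low stage 2 counts are each judged separately. With two-stage limits, 1/27 and 2/27 extend to 25.1% and 27.0% and no longer miss. The misses fall to 0.0238 + 0.0216 = 0.0454, a coverage of 95.5%.

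**5. Interval against decision rule.** The single-sample 95% interval includes the null at 5/26, marginally at 6/26, and at 4/27. It first excludes it at 7/26 (lower limit 11.6%) and 5/27 (6.3%). To separate the causes, change one thing at a time. Keeping 95% and adjusting for the stages leaves lower limits of 6.6% at 5/26 and 4.3% at 4/27, so the null is still included. Keeping the single-sample method and using 80% or 90% gives 9.7% at 5/26 and 5.2% at 4/27, so the null is excluded. The overlap at the thresholds comes from the confidence level.

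**The case against.** The strongest reply is that nothing decided in this trial depends on the interval. Success is a count, the error rates are as stated, and a two-sided 95% interval is a conventional estimation summary that need not match a phase II screening level. That stands. It also answers a stronger reading that a reader might infer: that a cohort declared promising beside an interval containing 9% or 5% is a contradiction. The documents do not support that. Worth further study, at an inferred one-sided 10% or 5%, is not a claim that the null is excluded at one-sided 2.5%. How often the two would appear together (0.32 in cohort 1 at the target, 0.16 in cohort 2) is a consequence of the chosen levels. In cohort 1 much of that figure rests on 6/26, where the limit misses 9% by 0.03 points.

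The reply also notes that the bias is small beside the sampling error: about half a point at the targets, against a root-mean-square error near 9 points. It adds that the planned interval is mostly conservative. Both are true. They limit the weight of the point but do not remove it, because the estimator of the primary objective is still biased in a known direction and the word exact does not hold for this design.

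**Conclusion.** The point holds as a shortcoming in estimation and reporting. The planned proportion is biased downward by 0.5 to 1.3 points at the design rates. The discrepancy is nearly 5 points at 2/26 and under 1 point at 5/26 and 4/27. The interval is conservative at the design rates and falls about one point short of 95% in a narrow band near a true rate of 25% in cohort 2. It would be wrong to call the interval generally invalid, to say the decision rule is undermined, or to blame the missing stage adjustment for the overlap with the null.

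The figures assume that exactly 16 then 26, and 13 then 27, patients are analysed and that the stopping rules are followed. The two-stage limits also depend on the ordering of outcomes stated above.

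**What to change.** In 11.3, for each cohort, report the UMVUE and an exact 95% interval based on the two-stage sample space, naming the ordering used, alongside the raw proportion. Add a sentence that the count rule alone (5 or more of 26, 4 or more of 27) governs the promising declaration. State that the 95% interval is descriptive and can include the null rate at 5/26 and 4/27 (and, for the single-sample version, marginally at 6/26), because the rule runs at one-sided 10% and 5%. State the sidedness explicitly in 11.2.

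An extra interval at the matching level (80% in cohort 1, 90% in cohort 2) is optional. With two-stage limits it gives 9.8% to 32.9% at 5/26 and 5.3% to 31.1% at 4/27.

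The cost is a few lines of text and code, with no change to patients, data or design. There is one statistical price: at the null the UMVUE has a slightly larger root-mean-square error than the raw proportion (6.7 against 6.1 points in cohort 1; 5.5 against 4.8 in cohort 2). At the target it is slightly smaller. Reporting both estimates covers this.

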### **2.2 Secondary Objectives**

- 2.2.1 To estimate the median progression-free survival (PFS) and 6-month PFS as defined by RECIST 1.1
- 2.2.2 To estimate the median, 1- and 2-year overall survival (OS)
- 2.2.3 To describe the safety and tolerability of combined trabectedin and olaparib

---

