#### **4.0 SUBJECT SCREENING AND REGISTRATION PROCEDURES**

Patient registration for this trial will be centrally managed by the Oncology Clinical Trials Support Unit (i.e. the Coordinating Center) of The University of Michigan Rogel Cancer Center as described below:

A potential study subject who has been screened for the trial and who has signed the Informed Consent document will be initially documented by the participating site on a Screening and Enrollment Log.

It is the responsibility of the local site investigator to determine patient eligibility prior to submitting patient registration request to the Coordinating Center. After patient eligibility has been determined, a copy of the completed Eligibility Worksheet together with all the pertinent redacted source documents will be submitted by the requesting site to the Coordinating Center, by email to [[contact]](mailto:[contact]).

A Multi-Site Coordinator of the Coordinating Center, who acts as the registrar, will review the submitted documents and process the registration. Sites should inform the Multi-Site Coordinator of a potential registration by 5 p.m. on the day prior to registration. Same day registrations cannot be guaranteed.

The registrar will send an email to the requesting site registrar to confirm patient registration and to provide the study identification number assigned to the patient. In addition, a copy of the

completed Eligibility Worksheet signed and dated by the registrar will be sent back to the requesting site registrar.

Patients found to be ineligible for participation after being consented will be considered screen failures and documented as such in the Screening and Enrollment Log. These patients will not have study identification number assigned to them and will not receive study treatment.

Patients will be enrolled to cohort 1 if they have a leiomyosarcoma or liposarcoma. All other sarcoma histologies will be enrolled to cohort 2. All patients receive the same treatment.

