### 7.2 **Safety/Tolerability**

Analyses will be performed for all patients having received at least one dose of study drug. The study will use the CTCAE version 5.0 for reporting of adverse events (<http://ctep.cancer.gov/reporting/ctc.html>).

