#### Olaparib

Adverse Events of Special Interest for olaparib are the Important Potential Risks of MDS/AML, new primary malignancy (other than MDS/AML) and pneumonitis.

A questionnaire will be sent to any investigator reporting an AESI, as an aid to provide further detailed information on the event. During the study there may be other events identified as AESIs that require the use of a questionnaire to help characterize the event and gain a better understanding regarding the relationship between the event and study treatment.

AESIs should not be reported as SAEs unless they meet the SAE reporting criteria per section 8.2.4.

Any AESI that is to be reported to Janssen and AstraZeneca by the Coordinating Center should be recorded on a Serious Adverse Event Report Form and be reported to Janssen and AstraZeneca **within 24 hours of knowledge of the event.**

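### Adverse events are tabulated by cohort only, and the 5% cut-off can drop single grade 1-2 events from both cohort tables, although all patients receive one regimen

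*Combined protocol and SAP*

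**What the plan says.** The safety objective in section 2.2 is "To describe the safety and tolerability of combined trabectedin and olaparib". It is stated for the combination, not by histology. Section 4.0 says of the two cohorts: "All patients receive the same treatment". Section 7.2 defines the safety set: "Analyses will be performed for all patients having received at least one dose of study drug".

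Section 11.3, secondary item c, then plans two summaries:

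- "The frequency and rates of adverse events occurring in at least 5% of participants";
- "rates of grade 3-5 adverse events will be tabulated by system organ class and preferred term".

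Both use "Common Terminology Criteria of Adverse Events (CTCAE), within each cohort". On the natural reading, the 5% limit belongs to the first summary only. The plan does not say whether the 5% is counted over a cohort or over the whole trial. It plans no adverse-event table across cohorts and no confidence intervals for adverse-event rates.

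Section 11.2 sets the denominators. For the first cohort: "In cohort 1, we require a minimum of 16 patients and a maximum of 26 patients". Cohort 2 has 13 to 27 patients. Section 8.2.2 states: "Adverse Events of Special Interest for olaparib are the Important Potential Risks of MDS/AML", and also names new primary malignancy and pneumonitis. Section 11.3 has no rule that shows these events whatever their count.

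**The concern.** The cohorts separate histologies with different historical response rates. That is a reason to split the efficacy analysis, but the plan gives no reason to split the description of one regimen's safety. Two consequences follow.

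First, a percentage cut-off on a table of about 26 patients works as a count rule: one patient is out, two are in. A mild or moderate event seen once in each cohort could be left out of both tables, and the reader could not tell that it had happened twice. A single low-grade pneumonitis could be left out of the summary in the same way. The count rule also depends on the efficacy result, because a cohort stopped after stage 1 is small enough for one patient to exceed 5%.

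Second, each reported rate rests on about half of the patients who received the regimen.

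**Working it through.** **Inputs.** Cohort sizes come from section 11.2: 16 (stage 1) and 26 (total) in cohort 1; 13 and 27 in cohort 2. At full accrual the pooled number is 26 + 27 = 53. The cut-off of 5% comes from section 11.3. The true incidences below are assumptions, because the documents give none for individual grade 1-2 terms under the combination.

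**Step 1: reproduce the plan's denominators.** An exact search for the Simon minimax design (smallest total with type 1 error within the limit and power of at least 80%, then smallest expected size under the null rate) returns the plan's designs:

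- Cohort 1 (9% against 25%, limit 10%): 16/26, stop if at most 1 response, success if at least 5. Type 1 error 0.0756, power 0.803.
- Cohort 2 (5% against 20%, limit 5%): 13/27, stop if 0 responses, success if at least 4. Type 1 error 0.0416, power 0.801.

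**Step 2: turn 5% into a count.** Find the smallest k with k/n at least 0.05.

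| n | 1/n | smallest k shown |
|---|---|---|
| 13 (cohort 2, stopped) | 7.7% | 1 |
| 16 (cohort 1, stopped) | 6.3% | 1 |
| 26 (cohort 1, full) | 3.8% | 2 (7.7%) |
| 27 (cohort 2, full) | 3.7% | 2 (7.4%) |
| 53 (pooled) | 1.9% | 3 (5.7%) |

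With a per-cohort cut-off and both cohorts full, the counts that occur but are not shown are (1,0), (0,1) and (1,1). If one cohort stops early, only a single event in the full cohort is hidden. If both stop, nothing is hidden.

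**Step 3: chance that a grade 1-2 term occurs but is in neither table.** Cohorts with no event must be excluded, because an absent event cannot be filtered out:

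P(hidden) = P(X1 ≤ 1 | 26, p) × P(X2 ≤ 1 | 27, p) − (1 − p)^53.

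At p = 5%: 0.624 × 0.606 − 0.066 = 0.312. Within one cohort, the chance of exactly one event is 26 × 0.05 × 0.95^25 = 0.361 for cohort 1 and 27 × 0.05 × 0.95^26 = 0.356 for cohort 2.

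For a 5% cut-off on the pooled column: P(X ≤ 2 | 53, p) − (1 − p)^53.

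| assumed p | cohort cut-off: occurs, in neither table | pooled 5% cut-off: occurs, not shown |
|---|---|---|
| 1% | 36% | 40% |
| 2% | 47% | 57% |
| 5% | 31% | 44% |
| 8% | 12% | 18% |

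The pooled cut-off is worse at every value. No pair of counts passes 5% pooled yet fails in both cohorts, whereas (2,0) and (0,2) pass by cohort and fail pooled. The threshold therefore causes the loss of terms, not the cohort layout.

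**Step 4: precision by cohort and pooled (exact Clopper-Pearson, 95%).**

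| | n = 26 | n = 27 | n = 53 |
|---|---|---|---|
| rate near 30% | 8/26, half-width 18.7 points | 8/27, 18.2 | 16/53, 13.0 |
| rate near 10% | 3/26, 2.4-30.2% | 3/27, 2.4-29.2% | 5/53, 3.1-20.7% |
| zero events, two-sided upper bound 1 − 0.025^(1/n) | 13.2% | 12.8% | 6.7% |

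**The case against.** The strongest reply is that little is lost. Much of it stands.

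- **Severe events.** A reader might infer that any adverse event seen once disappears. The text does not support this: the same sentence tabulates grade 3-5 events with no threshold, so a single severe event is kept. The loss is limited to grade 1-2 terms.
- **Monitoring.** A reader might also infer that events are lost to oversight. They are not. Section 8.1 puts every adverse event on the CRF whatever its grade or frequency, and sections 8.4 to 8.6 report SAEs individually. Section 8.2.2 gives events of special interest their own reporting route, and section 12.0 provides quarterly DSMC review. Cardiotoxicity has its own summary in section 11.3, without the 5% rule.
- **Precision.** All 53 patients are observed however the tables are laid out, so splitting does not reduce the chance of seeing an event. For grade 3-5 events a reader can add the two counts and recover the pooled rate exactly. Because no adverse-event intervals are planned, step 4 shows what a pooled estimate would offer rather than correcting a planned figure.
- **Denominator.** The 5% might be counted trial-wide, with the selected terms then shown by cohort. Any term shown could then be rebuilt. But the threshold would be 3/53, and more rare terms would be hidden (44% against 31% at 5% incidence). This reading moves the problem without removing it.
- **Cohort tables.** These are defensible: the designs are independent (section 11.1), and only cohort 1 requires a prior anthracycline (section 3.1.2), which could plausibly affect tolerability. That supports keeping cohort columns, but not leaving out the pooled one.

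**Conclusion.** The point holds as a gap in the planned safety summary. Section 11.3 answers an objective about one regimen with two separate tables and no pooled estimate, and its 5% rule can remove grade 1-2 terms. If the cut-off is counted per cohort and both cohorts fill, a term at a true 5% grade 1-2 incidence has about a 31% chance of occurring but being in neither table. The figure ranges from 12% to 47% over assumed incidences of 1% to 8%. In a cohort stopped at 16 or 13 patients, single events are shown.

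This rests on three assumptions: the 5% limit applies to the all-grade summary only, its denominator is the cohort, and patients' events are independent with the same incidence in both cohorts. The documents do not support a claim that severe events are suppressed, that events go unrecorded, or that patient safety monitoring is impaired. No efficacy estimate or decision rule changes.

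**What to change.** In section 11.3, secondary item c:

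1. Make the main safety table all treated patients pooled (up to 53), using the section 7.2 safety set, with the two cohorts as side columns.
2. List every adverse-event term of any grade with no frequency cut-off, and keep the grade 3-5 summary. This also removes the undefined denominator.
3. State that events of special interest (MDS/AML, new primary malignancy, pneumonitis) are always shown, whatever their count.

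Do not move the 5% cut-off to the pooled column: it would need three patients, and one event in each cohort (2/53 = 3.8%) would still be dropped.

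The data are already on the CRF, so no new visits, patients or collection are needed. The cost is one extra column and a longer table.
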